11.2.2 General summaries of TEAEs

Pre-treatment AEs will be provided in a subject data listing; no summaries of pre-treatment AEs are planned.

An overall summary of AEs will provide the overall number of TEAEs and the numbers and percentages of subjects with at least 1 TEAE, with a TEAE that led to permanent discontinuation of study drug, with a drug-related TEAE, with a severe TEAE, with a treatment-emergent SAE, and with a drug-related treatment-emergent SAE. The number and percentage of subjects who died will also be summarized. This summary will be provided for all subjects in the Safety Analysis Set and also by subgroup for geographic region and seizure type.

The following summaries of TEAEs will be provided by MedDRA SOC and PT. All summaries are for the combined Evaluation, Down-Titration, and Post-Treatment Periods unless otherwise indicated.

Overall Incidence Summaries

- Incidence of TEAEs
- Incidence of TEAEs by 3-month time interval
- Incidence of TEAEs by study period (Evaluation, Down-Titration, Post-Treatment)
- Incidence of TEAEs for TEAEs occurring in at least 5% of subjects
- Incidence of TEAEs by 3-month time intervals for TEAEs occurring in at least 5% of subjects overall
- Incidence of non-serious TEAEs occurring in at least 5% of subjects

The incidence of TEAEs occurring in at least 5% of subjects will be summarized overall as noted above and also by subgroup for geographic region, seizure type, and randomized treatment from the previous double-blind study.

A subject is included in a 3-month interval if the subject was receiving BRV at any time during that interval based on their duration of exposure to BRV (eg, a subject with exposure for 91 days is included in the time interval for Months 1-3 and Months 4-6). Summaries of AEs by 3-month intervals will include all subjects who are classified into each time interval

as defined above. TEAEs which had onset prior to or on the date of the last dose of BRV are included in summaries by 3-month time intervals.

Maximum Intensity and Causality

- Incidence of TEAEs by maximum intensity
- Incidence of drug-related TEAEs

Serious Adverse Events

- Incidence of treatment-emergent SAEs

Discontinuations due to TEAE

- Incidence of TEAEs leading to permanent discontinuation of study drug

TEAEs of interest

AEs of interest will be identified based on MedDRA search criteria, which are documented outside of the SAP. The following summaries will be provided for AEs of interest:

- Incidence of TEAEs of interest
- Incidence of TEAEs of interest by 3-month time interval

For the summary by maximum intensity, each subject will be counted at most once per SOC or PT according to the maximum intensity of all AEs within that SOC or PT. Severe intensity will be assumed for AEs for which intensity is not specified.

Drug-related AEs are AEs for which the relationship to study drug is specified as Related or AEs for which relationship is not specified.

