3.2.5 Monthly time intervals

A month is defined as 30 days and time intervals based on monthly durations are defined as a multiple of 30 days (eg, 12 months is defined as 360 days). The following definitions of 3-month and 6-month intervals are based on 30-day months where the date of first dose of BRV is Day 1:

| Interval | Duration Definition |
|--------------|---------------------|
| Months 1-3 | Days 1-90 |
| Months 4-6 | Days 91-180 |
| Months 7-9 | Days 181-270 |
| Months 10-12 | Days 271-360 |
| Months 1-6 | Days 1-180 |
| Months 7-12 | Days 181-360 |
| Months 13-18 | Days 361-540 |
| Months 19-24 | Days 541-720 |

Subsequent 3- and 6-month intervals are defined in a similar manner.

Six-month intervals are defined for the evaluation of direct and indirect cost parameters. Statistical summaries for direct and indirect cost parameters will only present results through the first 2 years of treatment. Three-month intervals will be used for analysis of efficacy outcomes and AEs.

End date is the date of last dose of BRV.

•

For the analysis of efficacy outcomes, a subject is included in the analysis for a 3-month interval if the end date is on or after the *last day* of the 3-month interval and the subject diary was completed for at least 1 day during the 3-month interval.

For the analysis of AEs, a subject is included in the analysis for a 3-month interval if the end date is on or after the *first day* of the 3-month interval.

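### The 3-month TEAE percentages count partly exposed subjects as whole ones, so incidence is understated by roughly half the share ending BRV in the interval, most in the final intervals at study closure

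*SAP*

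**What the plan says.** SAP 3.2.5 fixes the interval length: "A month is defined as 30 days and time intervals based on monthly durations are defined as a multiple of 30 days". A 3-month interval is therefore 90 days. For adverse events the same section includes a subject whose end date falls on or after the first day of the interval, and "End date is the date of last dose of BRV". The efficacy intervals use the opposite rule, an end date on or after the last day.

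SAP 11.2.2 repeats the AE rule ("A subject is included in a 3-month interval if the subject was receiving BRV at any time during that interval") and illustrates it: "a subject with exposure for 91 days is included in the time interval for Months 1-3 and Months 4-6". It limits the numerator: "TEAEs which had onset prior to or on the date of the last dose of BRV are included in summaries" by interval.

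Three sets of tables use this denominator: all TEAEs, TEAEs in at least 5% of subjects, and TEAEs of interest. SAP 11.1 plans subject-years overall, by modal dose and by subgroup, but not by interval. SAP 11.2.2 lists no exposure-adjusted AE rate. Protocol 13.1.3 plans TEAE tables by categories of total exposure duration; SAP 11.2.2 lists none.

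**The concern.** The denominator contains interval time in which no event can be counted. Subjects who end BRV inside an interval pull its percentage down although their AE rate while treated is unchanged. The amount depends on how many end there, so two intervals with the same underlying rate can show different percentages.

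This deserves attention because the primary objective is long-term safety and the 3-month tables are the only TEAE summaries in the SAP arranged by time on treatment. The table by study period separates evaluation, down-titration and post-treatment; it says nothing about early versus late exposure. If the last intervals are read at face value, a fall produced by treatment ending at closure could pass for better tolerability, and a real late rise would be diluted by the same factor.

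**Working it through.** **1. The SAP's own example.** 91 days of exposure is 90 days in Months 1-3 (Days 1-90) plus 1 day in Months 4-6 (Days 91-180). The example reproduces. In Months 4-6 this subject counts as 1 with 1/90 of the interval at risk.

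**2. Size of the bias in one interval.** The documents give no AE or retention rates, so both inputs are assumed. Let p be the risk of a first TEAE over a full 90 days and d the share of counted subjects ending BRV in the interval, with constant hazards:

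- a = -ln(1-p), m = -ln(1-d)
- SAP percentage = a/(a+m) × [1 - exp(-(a+m))]

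For p = 20% and d = 20%: a = m = 0.2231, so 0.5 × (1 - 0.64) = 18.0%, which is 10% below 20%. Other values at p = 20%:

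| d | SAP percentage | Relative error |
|---|---|---|
| 2% | 19.8% | -1.0% |
| 5% | 19.5% | -2.4% |
| 10% | 19.0% | -4.9% |
| 20% | 18.0% | -10.0% |
| 50% | 14.6% | -26.9% |
| 80% | 10.2% | -48.9% |

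The relative errors are similar at p = 5% (-1.0% to -50%) and p = 40% (-0.9% to -47%). A rough rule: if a share q ends at uniform times, observed time is 1 - q/2 of the full interval.

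**3. Does this create a trend?** With p flat at 20% over 12 intervals:

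- Constant d = 5%: 19.5% in every interval. No trend.
- Front-loaded dropout, d falling from 12% to 3%: 18.8% rising to 19.7%. Early intervals are the more understated.
- Closure tail, d = 10, 25, 50 and 80% in intervals 9-12: 19.0, 17.5, 14.6 and 10.2%. A spurious fall.

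**4. A worked closure scenario.** N = 668 (SAP 2.4). Assumed: uniform entry over 24 months, closure 72 months after first entry, dropout hazard 1.5% per month, constant TEAE hazard 5% per month. The full-interval risk is 1 - exp(-0.15) = 13.9%.

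| Interval | N counted | SAP percentage |
|---|---|---|
| 1-16 | 668 falling to about 340 | 13.6% throughout |
| 20 | about 178 | 12.3% |
| 22 | about 98 | 11.4% |
| 23 | about 63 | 10.3% |
| 24 | about 30 | 7.0% |

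The first four years are flat, about 2% low in relative terms. The shortfall starts at interval 17, when the latest entrants reach closure (72 - 24 = 48 months), and is about 8-10% relative in intervals 17-19. Intervals 20-24 hold about 4.7% of all exposure time. With binomial SE = sqrt(0.139 × 0.861/N), the shortfalls in intervals 20, 22, 23 and 24 are about 0.6, 0.7, 0.8 and 1.1 SE.

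**5. What person-time repairs, and what it does not.** In a simulation with true risk flat at 20% and closure spread over intervals 9-20, the SAP percentage reads 19.5% (interval 1), 18.6% (12), 16.5% (18) and 10.2% (20). The person-time estimate, converted to a 90-day risk, stays at about 19-20%. If instead AE risk varies between subjects (gamma variance 1), 10% of AEs cause withdrawal and there is no closure, the SAP percentage falls from 17.9% to 14.0% by interval 20 and the person-time estimate from 18.4% to 14.3%. That decline is selective dropout and remains after the change.

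Requiring exposure to the end of the interval is not a remedy. It drops subjects who stop because of an AE and gives 18.3% against a true 20%.

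**The case against.** The rule is open: it is stated in two sections with an example, and a percentage of subjects exposed in the interval is a legitimate descriptive quantity. It is understated only relative to a full 90-day risk, which the SAP does not claim to estimate. All summaries are descriptive, no AE trend analysis is planned, and the primary safety variables do not use this denominator. SAP 11.1 (numbers by exposure cohort) and SAP 5.1 (Kaplan-Meier estimates of time on treatment) let a reader see attrition. All of this stands and limits the importance of the point. It does not remove it: those tables do not give the time at risk behind each interval percentage.

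A reader might infer that late intervals are understated because they are late, so that AEs appear to decline over long-term treatment generally. The documents do not support that. The bias follows the share ending BRV within an interval, and no retention figures show that share rising except as treatment ends. In the scenario above, sixteen of 24 intervals are flat, and each of the four tail shortfalls quoted is about one standard error or less.

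A single closure date is also an assumption. Protocol 8.4 and 10.1.2 allow exit to another BRV study, commercial BRV or access programs by country, which would reshape the tail. Even so, everyone counted in the last populated interval ends in it, and the SAP states no cut-off for the AE intervals.

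**Conclusion.** The concern holds as a limited bias in the interval tables. The percentage is too low by roughly half the share ending BRV in the interval: 1-5% relative when 2-10% end, 10% at 20%, and up to about 50% when nearly all end. Steady dropout gives no trend. A spurious fall is expected only in the final, sparse intervals at closure, and its depth depends on assumed entry, dropout and closure patterns.

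The rule and the direction of the bias are certain from the text; the size in this trial is not. The overall TEAE, SAE and withdrawal incidences are unaffected. The change is a cheap improvement to how time on treatment is presented, not a correction to the primary results.

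**What to change.** In SAP 11.2.2, for each 3-month TEAE table, including TEAEs of interest:

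- Beside N, show BRV subject-time in the interval: days from interval start to the earlier of interval end and last dose.
- For any TEAE and for each SOC and PT row shown, add an exposure-adjusted incidence rate per 100 subject-years. The numerator is subjects with at least one such event in the interval. The denominator is time at risk in the interval, with each subject's time cut at the first such event in that interval, interval end or last dose, whichever comes first. This is a different denominator from the total subject-time beside N and should be labelled so.
- Keep the percentage and footnote that subjects with partial intervals are included.
- State that trends across intervals, by percentage or by rate, remain subject to selective dropout and should be read with the TEAE tables by total exposure duration planned in protocol 13.1.3. Those tables need to be listed in SAP 11.2.2 for this to be possible.

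The cost is SAP wording, wider tables and person-time programming specific to each row, from dose and AE onset dates already collected. Rates in the sparse late intervals will be unstable.

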#### **13.1.3 Statistical Evaluation**

- General considerations:

Summary statistics will consist of frequency tables for categorical variables and descriptive statistics (number of available observations, mean, median, standard deviation, minimum, maximum, 25th and 75th percentiles) for continuous variables.

The periods considered are:

- Evaluation Period (V1 until the last Evaluation Visit)
- Down-Titration Period
- Post-Treatment Period

Efficacy summaries will be created separately for the POS and PGS subpopulations within the efficacy population, and safety summaries will be created for the safety population.

- Baseline:

Baseline, whether efficacy or safety, will always refer to the original prior study pretreatment Baseline value. Baselines created and validated, as part of the prior study SAPs, will be copied and used by this study for all changes from baseline analyses.

- Study entry/disposition:

Subjects will be sufficiently described to enable a clear understanding of the populations and subpopulations and relevant demographics, disease, medical history, current treatment(s), as well as disposition. Historical and Baseline data will be copied from the prior study as required by the SAP.

- Seizure efficacy variables:

Analyses will be based upon the Efficacy Population. Summaries will be over the entire Evaluation Period and by 3-month periods over the Evaluation Period.

- QOLIE-31-P, HADS, EQ-5D, and socio-professional efficacy variables:

Analyses will be based upon the Efficacy Population and summarized by data collection scheduled visits and for the last Evaluation Period assessment during the first 2 years. Data collected after Year 2 are not planned to be summarized.

- Medical resource and indirect cost efficacy variables:

Analyses will be based upon the Efficacy Population and summarized by 3-month periods. Data collected after Year 2 are not planned to be summarized.

- Safety variables:

Analyses will be based upon the Safety Population. Summary tables will be presented over the Evaluation Period by time windows, by periods, and by categories of total duration of exposure.

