Treatment-emergent AEs will be summarized by categories of total duration of exposure, period, and Medical Dictionary for Regulatory Activities (MedDRA®) Primary System Organ Class (SOC), and Preferred Term in incidence tables. Separate tables will be provided by categories of total duration of exposure, for AEs leading to withdrawal from the study, and for SAEs.

This document contains information used to support all marketing authorization applications and any extensions or variations thereof.

Laboratory values, vital signs, and weight will be summarized by period and visit. Possibly clinically significant treatment-emergent abnormalities for laboratory values, vital signs, and weight will be listed and summarized by period and visit. Electrocardiogram abnormalities, as well as physical and neurological abnormalities, will also be listed by period and visit.

Hospital anxiety and depression scales will be analyzed for the POS and PGS subpopulations.

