### **13.3 Statistical and Analytical Issues**

#### ***13.3.1 Handling of Dropouts of Missing Data***

Safety and efficacy variables will be analyzed as they are available. Days with missing information will be ignored in the calculation of the seizure frequency and seizure days. Since subjects will drop out at different times from the study, results will be presented by categories of duration of exposure.

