3.2.4 Study periods

The study is divided into 3 periods: Evaluation Period, Down-Titration Period, and Post-Treatment Period. A subject is classified as “discontinued” if the subject has a termination case report form (CRF) or has an early discontinuation visit (EDV). A subject is classified as “completed” if this subject completes the full extent of the study as defined in the protocol at database lock.

A “discontinued” subject can be potentially slotted into the 3 periods of the study. The following algorithms will be used to slot the subject appropriately into the Evaluation Period, Down-Titration Period, and Post-Treatment Period.

- For Evaluation Period, the start date is the date of first dose of BRV, and the following algorithm is used to determine the end date:
 - If the subject enters the Down-Titration Period, then the date of EDV is the end date;
 - If the subject does not enter the Down-Titration Period but meets 1 of the following criteria, the Evaluation Period ends on date of last dose of BRV:
 - Without an EDV but having a termination CRF,
 - With an EDV and having a termination CRF,
 - With an EDV and the date of EDV prior to the database lock date and having no termination CRF.
- A subject is considered entering Down-Titration Period only if the subject has an EDV and at least 1 dose of study drug after the date of EDV, the start date of Down-Titration Period is set as 1 day after the date of EDV, and the Down-Titration Period ends on date of last dose of BRV. A subject without an EDV but having a termination CRF or with an EDV but without any dosing of study drug after the EDV will not have the Down-Titration Period, and no artificial Down-Titration Period will be created for analysis.
- A subject is considered entering the Post-Treatment Period if the subject has at least 1 contact (scheduled visit, unscheduled visit, or telephone contact) after the date of last dose of BRV. The Post-Treatment Period starts 1 day after date of last dose of BRV irrespective of entering the Down-Titration Period, and there is no end date.

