3.2.7 Exposure duration and exposure duration cohorts

At the final analysis, the overall duration of exposure (or On Treatment Period) will be calculated as the date of last dose of BRV minus the date of first dose of BRV plus 1 day.

Each subject will be classified into one or more of the following exposure duration cohorts based on the duration of BRV exposure as calculated above:

| | |
|--------------|-----------|
| All subjects | ≥1 day |
| ≥3 months | ≥90 days |
| ≥6 months | ≥180 days |
| ≥12 months | ≥360 days |

This categorization will continue in 6-month increments past 12 months up to a time point that will be determined based on cumulative exposure at the time of the database lock.

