4.2 Handling of dropouts or missing data

Seizure frequency (subjects with POS) and seizure days (subjects with PGS) will be calculated over non missing diary days during each study period or time interval as described in Section 3.2.4 and Section 3.2.5 ; diary days for which seizure data were not obtained will not be considered in the calculation of seizure frequency or seizure days. Because the evaluation of efficacy is not the primary objective of this study, and because this is an uncontrolled study in a variable setting, which allows individualized optimization of dosing of BRV and concomitant AEDs, no summaries assessing the impact of missing seizure diary days are planned.

For subjects who prematurely discontinue during the Evaluation Period, the calculation of POS frequency and PGS seizure days will be based on available seizure diary while the subject was receiving BRV. The presence of such dropouts may influence the evaluation of the long-term outcomes for subjects who either do not discontinue or do not discontinue early in the study. Therefore, as described below, selected summaries will be produced by exposure duration cohorts to allow an assessment of long-term outcomes without the potentially confounding influence of earlier discontinuations.

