Kaplan-Meier estimates of the percentage of subjects completing 3, 6, 12, 24, 36, 48, and 60 months of treatment with BRV will be provided. This analysis will be based on the duration of exposure to BRV as defined in Section 3.2.7. Subjects who have permanently discontinued will be analyzed as events on the last day of treatment with study drug; subjects who complete the study will be censored on the last day of treatment with study drug.

The date of first subject in (date of earliest Visit 1), date of last subject out (date of last scheduled or unscheduled visit), number of enrolled subjects, and the number of subjects in each analysis set or seizure type will be summarized overall and by investigator site.

Subjects who transferred sites will be summarized according to their original site.

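### The SAP drops, without explanation, the protocol's adverse-event tables by duration of exposure, and leaves SAEs and TEAEs leading to discontinuation as crude percentages only

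*SAP*

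**What the plan says.** **Protocol.** Section 13.1.3 states for safety variables generally: "Summary tables will be presented over the Evaluation Period by time windows, by periods, and by categories of total duration of exposure". It repeats the duration categories for TEAEs and continues: "Separate tables will be provided by categories of total duration of exposure, for AEs leading to withdrawal from the study, and for SAEs". Section 13.3.1 gives the reason: "Since subjects will drop out at different times from the study, results will be presented by categories of duration of exposure".

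**SAP, exposure cohorts.** Section 3.2.7 sets up the tool: "Each subject will be classified into one or more of the following exposure duration cohorts". The cohorts are minimum-exposure sets (at least 1 day, then at least 3, 6 and 12 months, then 6-month steps), so they are nested. Section 4.2 says selected summaries will use them "to allow an assessment of long-term outcomes without the potentially confounding influence of earlier discontinuations". The later sections apply them to seizure outcomes (8.1, 8.2) and to exposure and modal dose (11.1).

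**SAP, adverse events.** Section 11.2.2 has no table by exposure cohort. Tables by 3-month interval are planned for all TEAEs, for TEAEs in at least 5% of subjects and for TEAEs of interest. Treatment-emergent SAEs and discontinuation TEAEs each get a line in the overall summary (also by region and seizure type) and one SOC/PT table, the second being "Incidence of TEAEs leading to permanent discontinuation of study drug". Evaluation, Down-Titration and Post-Treatment Periods are pooled. Section 3.2.4 starts the Post-Treatment Period the day after the last dose, "irrespective of entering the Down-Titration Period, and there is no end date".

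**SAP, related displays.** Section 5.1 plans "Kaplan-Meier estimates of the percentage of subjects completing 3, 6, 12, 24, 36, 48, and 60 months" of treatment, for discontinuation from any cause, and counts adverse event as a discontinuation reason. Section 11.1 tabulates subject-years, also by region and seizure type.

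**The concern.** The primary objective is long-term safety, and exposure will range from a single day to at least the 60 months at which retention is to be estimated. Under such follow-up, the percentage of subjects who ever had an SAE mixes the event rate with the time people stayed. It cannot show whether the risk of an SAE, or of stopping because of an adverse event, falls, stays level or rises with longer treatment. Region and seizure-type contrasts could also be distorted if follow-up differs between the groups; the documents do not say whether it does.

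The SAP accepts this argument for seizure outcomes, which are secondary, but does not carry it over to two primary safety variables. The SAP amendment (section 14) explains dropping the interim-cutoff rules and the cost and socio-professional summaries, and is silent on these tables.

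**Working it through.** **1. Protocol against SAP.**

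| Display | Protocol 13.1.3 / 13.3.1 | SAP 11.2.2 |
|---|---|---|
| TEAEs by exposure duration | promised | none |
| SAEs by exposure duration | promised | none |
| Withdrawal AEs by exposure duration | promised | none |
| SAEs or discontinuation TEAEs by 3-month interval | not specifically promised | none |
| Any AE rate per subject-year | not promised | none |

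Only the first three rows depart from the protocol. The last two are gaps in method.

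**2. Effect of follow-up time alone.** The documents give no event or dropout rate to reproduce, so every rate below is an assumption. With a constant first-event rate r and complete follow-up t, crude incidence is 1 − exp(−rt).

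- r = 0.03 per subject-year: 1 − exp(−0.03) = 3.0% at 1 year; 1 − exp(−0.15) = 13.9% at 5 years.
- r = 0.10: 1 − exp(−0.10) = 9.5%; 1 − exp(−0.50) = 39.3%.

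**3. Subgroups with equal risk.** Let dropout be exponential at rate d, independent of the event, with follow-up capped at T = 5 years.

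- Crude incidence = r/(r+d) × [1 − exp(−(r+d)T)]
- Mean total exposure = [1 − exp(−dT)]/d

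| d per year | Mean exposure (years) | Crude, r = 0.03 | Crude, r = 0.10 |
|---|---|---|---|
| 0.15 | 3.52 | 9.9% | 28.5% |
| 0.20 | 3.16 | 8.9% | 25.9% |
| 0.25 | 2.85 | 8.1% | 23.6% |
| 0.30 | 2.59 | 7.3% | 21.6% |
| 0.40 | 2.16 | 6.2% | 18.4% |

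Ratios of crude incidence between two groups with the same r:

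- equal dropout: 1.00
- 0.25 against 0.20: 1.10
- 0.30 against 0.15: 1.35 (r = 0.03) and 1.32 (r = 0.10)
- 0.40 against 0.20: 1.45 and 1.41

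**4. What a rate returns.** First events divided by subject-years to first event or last dose give 3.0 or 10.0 per 100 in every row. First events divided by the total subject-years of SAP 11.1 give 2.81 to 2.85 for a true 3.0 (about 5–6% low) and 8.11 to 8.49 for a true 10.0 (15–19% low), because time after the event is still counted.

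**5. Timing.** With d = 0.20 and T = 5, a constant rate of 0.10 gives 25.9%. A rate of 0.60 for the first 3 months and about 0.055 afterwards gives the same 25.9%. The crude figure cannot tell these apart.

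**6. Nested cohorts and AE withdrawal.** With total dropout of 0.20 per year, of which AE withdrawal is a constant part, and a 5-year cap, the share of AE withdrawals falling in year 1 is [1 − exp(−0.20)]/[1 − exp(−1.00)] = 0.181/0.632 = 29%. None of them can be in a cohort with at least 12 months of exposure.

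**The case against.** The strongest points on the other side are these.

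- **The variables are binary.** Occurrence of an SAE and withdrawal due to an AE are summarised directly by a number and a percentage in a descriptive single-arm study. That is fair, and the percentages should stay, but alone they do not describe risk over time.
- **Rates and 3-month SAE tables were never promised.** Correct. They are recommended as better method, separately from the departure from the protocol.
- **The protocol sentence on withdrawals and SAEs is ambiguous.** It could mean three separate kinds of table. Even so, the general safety sentence, the TEAE sentence and section 13.3.1 still call for duration categories.
- **The SAP does handle time for adverse events.** Section 3.2.5 sets a 3-month rule, and 11.2.2 uses it for all TEAEs. Those tables include serious and discontinuing events without separating them. The Kaplan-Meier estimates are all-cause, and the counts of AE as a discontinuation reason carry no time.
- **A rate can be approximated from planned output.** Dividing counts by the subject-years in section 11.1 removes most of the subgroup contrast, but reads low by the amounts shown, and the numerators include post-treatment events.
- **The open-ended Post-Treatment Period matters little.** The Final Visit follows 2 to 4 weeks off drug, and routine SAE reporting runs to 30 days. This limits the problem. The stated definition still has no end, and events suspected to be related are reportable without a time limit.
- **The sizes are hypothetical.** They are. Ratios of 1.3 or more come from a twofold dropout difference that nothing in the documents establishes.

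**Conclusion.** The concern holds. That the by-duration adverse-event tables are missing and unexplained follows from the text alone. The further gap, that SAEs and discontinuation TEAEs have neither a 3-month table nor a rate, is a weakness of method for a long-term safety objective.

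Its size cannot be taken from the documents. Under the assumed rates, follow-up time alone moves the crude percentage about four- to fivefold between 1 and 5 years. Subgroup distortion runs from none with equal dropout to about 1.4-fold with a twofold dropout difference. These figures rest on constant event and dropout rates and on dropout unrelated to the event. The change should be made; the planned analyses remain usable as descriptive summaries without it.

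**What to change.** In SAP 11.2.2:

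1. **Rates.** For any TEAE, SAE, TEAE leading to discontinuation, and death, add the incidence rate per 100 subject-years with a 95% CI, overall and by region and seizure type. The numerator is subjects with a first event between first and last dose; the denominator is subject-years to first event or last dose. Report events after the last dose separately.
2. **Time pattern.** Add 3-month-interval tables for SAEs and discontinuation TEAEs, using the inclusion rule already in 11.2.2.
3. **The protocol's tables.** Provide TEAEs and SAEs by exposure-duration category, or record and justify the departure. For AE withdrawal, do not rely on the nested cohorts of 3.2.7, because withdrawal itself sets the duration. Use the rate in item 1, or a cumulative incidence with other discontinuations as competing events, and state this as the reason for the change.

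The cost is a few more tables and one new derivation, time to first event, from existing AE and dosing dates. The rate assumes a roughly constant hazard, which the tables in item 2 let the reader check. The drawback is more output.
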